6.1.5 End-of-stimulation

The end-of-stimulation visit will take place when the subject reaches the criterion for triggering of final follicular maturation or if the cycle is canceled. Administration of hCG or GnRH agonist must take place the same day as the criterion for triggering of final follicular maturation, i.e. ≥ 2 follicles with a diameter of ≥ 17 mm, is met. Administration of FE 999049 or placebo after reaching the triggering criterion is not allowed.

Criterion for triggering of final follicular maturation with 10,000 IU hCG:

• <20 follicles with a diameter of \geq 12 mm

Date: 25 Apr 2018 E-Study Protocol-22377; Ver. 1.0 Supersedes: None Page 75 of 159

Criterion for triggering of final follicular maturation with 4 mg GnRH agonist:

• ≥20 follicles with a diameter of ≥12 mm or serum estradiol concentration ≥3,000 pg/mL (local laboratory)

If after 8 days of stimulation, the investigator judges that the triggering criterion, i.e. ≥ 2 follicles with a diameter of ≥ 17 mm, is not likely to be reached by day 20, the cycle will be canceled. If the triggering criterion is not met after 20 days of stimulation, the cycle will be canceled.

The investigator also has the option of canceling the cycle for other relevant medical reasons, including adverse events and technical malfunctions of the administration pen. In the latter event, the option of replacing the administration pen and continuing treatment should be considered.

The following must take place at end-of-stimulation visit:

- Transvaginal ultrasound of uterus (endometrial thickness, echogenicity pattern) and ovaries (number and size of follicles, ovarian volume)
- Blood collection for central laboratory analysis of:
 - clinical chemistry and hematology parameters
 - endocrine parameters (AMH, FSH, LH, estradiol, progesterone, inhibin A and inhibin B) –
 the blood sample must be drawn at least 8 hours after the latest administration of IMP and GnRH antagonist
- Blood collection for local laboratory analysis of estradiol (used to determine the triggering drug)
- Dispensing of hCG or GnRH agonist, as applicable
- Collection of local tolerability data (diary pages)
- Drug accountability of IMP and GnRH antagonist
- Recording of use of any concomitant medication
- Recording of adverse events

For subjects who receive a triggering drug, the next visit is the oocyte retrieval visit which must be scheduled $36h (\pm 2h)$ after the administration of hCG or GnRH agonist.

For subjects with cycle cancellation, the next visit is the first post-dosing anti-FSH antibody blood sampling visit 7-10 days after the last FE 999049 or placebo dose (section 6.1.8.2).

Date: 25 Apr 2018 E-Study Protocol-22377; Ver. 1.0 Supersedes: None Page 76 of 159

6.1.6 Oocyte Retrieval

Oocyte retrieval must take place 36h (\pm 2h) after hCG or GnRH agonist administration. All oocytes from follicles with an estimated diameter of \geq 12 mm should be retrieved. The procedures related to subjects attending the oocyte retrieval visit are listed below, while procedures related to the oocytes are described in section 6.1.7.

The following must take place at the oocyte retrieval visit:

- Blood collection for central laboratory analysis of:
 - endocrine parameters (AMH, FSH, LH, estradiol, progesterone, inhibin A and inhibin B)
- Oocyte retrieval
- Dispensing of progesterone vaginal inserts for luteal phase support must be started on the day after oocyte retrieval [note: only applicable for subjects who underwent triggering of final follicular maturation with hCG and who had oocytes retrieved]
- Drug accountability of hCG or GnRH agonist, as applicable
- Recording of use of any concomitant medication
- Recording of adverse events

For subjects with <20 oocytes retrieved following hCG administration, the next visit is the transfer visit 5 days after oocyte retrieval (section 6.1.8.1).

For subjects with \geq 20 oocytes retrieved following hCG administration and for subjects with oocytes retrieved following GnRH agonist administration the fresh blastocyst transfer will be canceled. The oocytes will undergo the procedures described in section 6.1.7 and blastocysts will be cryopreserved by vitrification. The next visit for these subjects is the first post-dosing anti-FSH antibody assessment visit which must be scheduled 7-10 days after the last FE 999049 or placebo dose (section 6.1.8.2).

For subjects with no oocytes retrieved, the next visit is the first post-dosing anti-FSH antibody assessment visit which must be scheduled 7-10 days after the last FE 999049 or placebo dose (section 6.1.8.2).

6.1.7 Oocyte / Blastocyst Evaluation

The laboratory procedures regarding handling and evaluations of oocytes and blastocysts are described in a trial-specific manual. This section provides an overview of the procedures and assessments to be made from oocyte retrieval until transfer at the blastocyst stage. The flow of the trial procedures for

Trial Code: 000002 Date: 25 Apr 2018 E-Study Protocol-22377; Ver. 1.0

> Supersedes: None Page 77 of 159

oocytes is shown in Table 6-2.

Table 6-2 Trial Flow Chart – Oocyte / Blastocyst Procedures

	Day 0 (OR)		Day 1 after OR	Day 5 after OR
Timing	-4h (±1h)	0h	19h (±2h)	Day 5
Oocyte retrieval (OR)	X			
Assessment of maturity stage (applicable for oocytes undergoing ICSI)	X			
Insemination by IVF and/or ICSI		X		
Assessment of oocyte fertilization			X	
Assessment of blastocyst quality				X
Transfer of one or two blastocysts of the highest quality available: - Subjects with at least one good-quality blastocyst (i.e. grade 3BB or above) will have one blastocyst transferred - Subjects with no good-quality blastocysts available (i.e. lower than grade 3BB) will have one or two blastocysts transferred				X
Cryopreservation of blastocysts by vitrification, as applicable				Xa

^a In case the embryologist judges that a blastocyst/morula is still developing, continued culturing and cryopreservation on day 6 is allowed. ICSI: intracytoplasmic sperm injection; IVF: in vitro fertilization; OR: oocyte retrieval

Blastocyst biopsy, assisted hatching and PGD/PGS are prohibited.

Day 0 (Oocyte Retrieval)

- Oocyte retrieval at 4h (\pm 1h) before start of the insemination procedure
- Assessment of maturity stage (applicable for oocytes undergoing ICSI)
- Insemination at 0h using IVF or ICSI using ejaculated sperm (fresh or frozen) from partner or donor

Day 1 after Oocyte Retrieval

• Assessment of fertilization (number of pronuclei) at 19h (±2h) post-insemination

Day 5 after Oocyte Retrieval

Assessment of blastocyst quality

Trial Code: 000002 Date: 25 Apr 2018 E-Study Protocol-22377; Ver. 1.0

Supersedes: None Page 78 of 159

- Transfer of blastocyst(s) (section 6.1.8.1)
- Cryopreservation of blastocysts by vitrification, as applicable. In case the embryologist judges
 that a blastocyst/morula is still developing, continued culturing and cryopreservation on day 6
 is allowed

6.1.8 Transfer

6.1.8.1 Blastocyst Transfer

Transfer is performed on day 5 (blastocyst stage) after oocyte retrieval. Transfer of day 6 (or later) blastocysts is not allowed in the fresh cycle.

The subject-related procedures are described below.

- Blood collection for central laboratory analysis of anti-FSH antibodies (first post-dosing assessment)
- Tongue coat collection for future potential microbial profiling (applicable for subjects who have provided a separate informed consent)
- Transfer of one or two blastocysts of the highest quality available (per judgement of the site embryologist):
 - Subjects with at least one good-quality blastocyst (i.e. grade 3BB or above^a) will have one blastocyst transferred
 - Subjects with no good-quality blastocysts available (i.e. lower than grade 3BB) will have one or two blastocysts transferred
- Dispensing of progesterone vaginal inserts for luteal phase support, if applicable
- Drug accountability of progesterone vaginal inserts
- Recording of use of any concomitant medication
- Recording of adverse events

For subjects with blastocyst transfer, the next visit is the β hCG test visit which must be scheduled 10-14 days after transfer (section 6.1.9.1).

¹ 3BB and above defined as: 6AA, 6AB, 6AC, 6BA, 6BB, 6BC, 6CA, 6CB, 6CC, 5AA, 5AB, 5AC, 5BA, 5BB, 5BC, 5CA, 5CB, 5CC, 4AA, 4AB, 4AC, 4BA, 4BB, 4BC, 4CA, 4CB, 4CC, 3AA, 3AB, 3AC, 3BA, or 3BB.

Date: 25 Apr 2018 E-Study Protocol-22377; Ver. 1.0 Supersedes: None Page 79 of 159

6.1.8.2 First Post-dosing Anti-FSH Antibody Assessment (7-10 Days after Last IMP Dose)

Subjects who have been exposed to FE 999049 or placebo must have the first post-dosing anti-FSH antibody assessment performed 7-10 days after the last FE 999049 or placebo dose. This may coincide with the transfer visit (section 6.1.8.1).

For subjects who do not attend the transfer visit, a separate visit must be scheduled, at which the following must take place:

- Blood collection for central laboratory analysis of anti-FSH antibodies
- Drug accountability of progesterone vaginal inserts, if applicable
- Recording of use of any concomitant medication
- Recording of adverse events

6.1.9 BhCG Test

6.1.9.1 βhCG Test

Subjects who have undergone transfer must attend a visit 10-14 days after transfer.

The following must take place:

- Blood collection for local laboratory analysis of βhCG
- Blood collection for central laboratory analysis of anti-FSH antibodies (second post-dosing assessment)
- Dispensing of progesterone vaginal inserts, if applicable
- Drug accountability of progesterone vaginal inserts
- Recording of use of any concomitant medication
- Recording of adverse events

The blood sample for β hCG will be analyzed by the local laboratory and evaluated according to the local reference ranges. In case of a doubtful / inconclusive β hCG result, the test may be repeated, preferably within 2 days, and the conclusive result recorded. Subjects with a positive β hCG test must attend a clinical pregnancy visit 5-6 weeks after transfer (section 6.1.10). Subjects with a negative β hCG test must proceed to the end-of-cycle assessments (section 6.1.12).

Date: 25 Apr 2018 E-Study Protocol-22377; Ver. 1.0 Supersedes: None Page 80 of 159

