Clinical safety endpoints cover adverse events, clinical chemistry and hematology parameters, local tolerability, immunogenicity, OHSS and pregnancy-related events (i.e. multi-fetal gestations, biochemical pregnancies, spontaneous abortions, ectopic pregnancies and vanishing twins). Predefined local tolerability reactions, i.e. redness, pain, itching, swelling and bruising, will be assessed by the subjects on three occasions after each subcutaneous IMP injection spanning from immediately to 24 hours after. Presence of anti-FSH antibodies will be evaluated 7-10 and 21-28 days after the last administration of FE 999049 for assessment of a potential immunoglobulin M (IgM) response and a fully mounted immunoglobulin G (IgG) immune response, respectively. ¹⁵ Technical malfunction of the pens used for administration of FE 999049 and placebo will also be monitored.

Live birth is the ultimate objective for couples starting infertility treatment. Nevertheless, it can be justified to use ongoing pregnancy rate as an endpoint indicative of the final treatment outcome as few pregnancy losses occur after confirmation of ongoing pregnancy. ¹⁶ In the ESTHER-1 trial, the absolute difference between live birth rate and ongoing pregnancy rate was -0.7% among the women aged ≥35 years. In the present trial, ongoing pregnancies in the fresh and cryopreserved cycles will be followed until live birth, allowing for evaluation of cumulative live birth rate. Neonatal health data at birth, 4 weeks and 1 year after birth will be collected for infants born after the fresh cycle and cryopreserved cycles to provide additional safety information.

In conclusion, the primary and secondary endpoints are appropriate for a phase 3 trial designed to document the efficacy and safety of a gonadotropin intended for controlled ovarian stimulation.

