6 TRIAL PROCEDURES

6.1 Controlled Ovarian Stimulation and Fresh Cycle

The flow of the trial procedures for subjects in the controlled ovarian stimulation and fresh cycle is shown in Table 6-1.

Trial Code: 000002 Date: 25 Apr 2018 E-Study Protocol-22377; Ver. 1.0

> Supersedes: None Page 69 of 159

Trial Flow Chart - Subject Procedures - Controlled Ovarian Stimulation and Fresh Table 6-1

	Screening	ng Stimulation				OR	Transfer	Pregnancy monitoring			End
	, ,	Du	ring stimu	lation	End-of- stimula -tion	retrieval	Transfer	βhCG	Clinical	Ongoing	End-of- cycle
Timing	<90 days before ran- domization	Day 1	Day 5	Day ≥6 to <20 a)	End	36h ±2h after triggering	Day 5 after OR	10-14 days after transfer	5-6 weeks after transfer	8-9 weeks after transfer	ь)
Written informed consent(s)	X										
Inclusion/exclusion criteria	X	X c)									
Demographics	X										
Medical history	X										
Infertility history	X										
Menstrual history	X										
Reproductive history	X										
Body measurements	X	X c,d)									X d)
Physical examination	X										X
Gynecological examination	X										X
Urine pregnancy test	X	X c)									
Ultrasound sonography ^{e)}		X c)	X	X	X				X	X	
Randomization		X									
Vital signs	X	X f)									X
Blood collection, clin chem / hem	X				X						X
Blood collection, endocrine	X	X f)	X g)		X g)	X					
Blood collection, antibodies h)	X i)	X f)					X ^{j)}	X k)			X k)
Blood collection, estradiol			X	X	X						
Blood collection, genome 1)		X									
Saliva collection, genome 1)		X									
Tongue coat collection, microbiome 1)		X					X				
IMP dispensing		X	X m)	X m)							
NIMP dispensing			X n)	X	X	X	X	X	X		
Local tolerability (diary)		X	X	X	X						
Oocyte retrieval						X					
Blastocyst transfer / cryo							X				
βhCG test (local lab)								X			
Drug accountability			X	X	X	X	X	X	X	X	X
Concomitant medication	X	X	X	X	X	X	X	X	X	X	X
Adverse events	X	X	X	X	X	X	X	X	X	X	X
End-of-cycle form											X

Visits must be scheduled at least every second day; when the leading follicle reaches ≥14 mm visits must be performed daily. End-of-cycle assessments must be performed at the subject's last scheduled visit: at the earliest 21-28 days after the last IMP dose. Performed before randomization. Only body weight.

Transvaginal ultrasound with exception of the ongoing pregnancy visit, where it can be either transvaginal or abdominal ultrasound. Performed before the first IMP dose.

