Performed at least 8 h after IMP administration (and NIMP administration at end-of-stimulation visit).

All subjects with a treatment-induced antibody response must be followed until the response is negative or has returned to pre-dosing level. Sample exclusively used to re-establish the anti-drug antibody analytical assays.

Blood sampling for antibody assessment must be done 7-10 days after the last IMP dose (this may coincide with the transfer visit; alternatively,

a separate visit must be scheduled).
 k) Blood sampling for antibody assessment must be done 21-28 days after the last IMP dose (this may coincide with the βhCG test visit; alternatively, a separate visit must be scheduled).

Optional sampling for future potential exploratory analyses for subjects who have provided separate written informed consent. The starting dose of 15 µg FE 999049 is fixed for the first 4 stimulation days. Based on the ovarian response, the daily dose may be adjusted by 3 µg, with dose increases implemented not more frequently than once every 2 days and dose decreases implemented per investigator's judgement. The

minimum dose is 6 µg, and the maximum dose is 24 µg.

GnRH antagonist will be initiated on stimulation day 5 for subjects with \geq 3 follicles with a diameter of \geq 10 mm. Subjects who fail to satisfy this GnRH antagonist criterion on stimulation day 5 will continue to be monitored at least every second day, and GnRH antagonist will be initiated when/if the criterion is met.

βhCG: β human chorionic gonadotropin; IMP: investigational medicinal product; NIMP: non-investigational medicinal product; OR: oocyte retrieval

Date: 25 Apr 2018 E-Study Protocol-22377; Ver. 1.0 Supersedes: None Page 70 of 159

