6.1.9.2 Second Post-dosing Anti-FSH Antibody Assessment (21-28 Days after Last IMP Dose)

Subjects who have been exposed to FE 999049 or placebo must have the second post-dosing anti-FSH antibody assessment performed 21-28 days after the last FE 999049 or placebo dose. This may coincide with the β hCG test visit (section 6.1.9.1).

For subjects who do not attend the β hCG test visit, this second post-dosing anti-FSH antibody assessment may be done in connection with the end-of-cycle assessments (section 6.1.12) if applicable or a separate visit must be scheduled, at which the following must take place:

- Blood collection for central laboratory analysis of anti-FSH antibodies
- Drug accountability of progesterone vaginal inserts, if applicable
- Recording of use of any concomitant medication
- Recording of adverse events

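### The protocol orders the second anti-FSH antibody sample at the βhCG visit without a day condition, although most permitted days for that visit fall before the required 21-28 day sampling window

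*Protocol*

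**What the plan says.** Four places in the protocol govern the second post-dosing antibody sample.

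- **Section 6.1.9.1 (βhCG visit, 10-14 days after transfer).** Among the items that have to be done at the visit is "Blood collection for central laboratory analysis of anti-FSH antibodies (second post-dosing" assessment). No number of days since the last dose is attached.
- **Section 6.1.9.2.** All exposed women need the "antibody assessment performed 21-28 days after the last FE 999049 or placebo dose". It may coincide with the βhCG visit. For women who do not attend that visit, the draw may be made at end-of-cycle or at a separate visit.
- **Table 6-1, footnote k.** "Blood sampling for antibody assessment must be done 21-28 days after the last IMP dose". This may coincide with the βhCG visit; otherwise a separate visit has to be scheduled.
- **Section 6.1.12.** End-of-cycle assessments cannot precede the 21-28 day point. The second antibody sample is drawn there only if it has not already been taken.

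Section 7.2.4 repeats the 21-28 day window and gives the end-of-cycle alternative for women who discontinue before the βhCG visit. Section 3.5.2 explains the two post-dosing samples: they are timed "for assessment of a potential immunoglobulin M (IgM) response and a fully mounted immunoglobulin G (IgG) immune response", in that order.

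SAP 10.5 tabulates the proportions with treatment-induced and with neutralizing antibodies, and lists all assessments for subjects positive in assay 2. It does not refer to when a sample was drawn.

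**The concern.** The first post-dosing sample fits the visit it is paired with: transfer falls about 7-8 days after the last dose, inside its 7-10 day window. The second pairing mostly does not fit. A site working from the visit checklist in 6.1.9.1 would draw the sample at whatever βhCG day it had booked, and on most of those days the draw would be early by the standard of footnote k.

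The later window was chosen for a mature IgG response. A woman negative at both the 7-10 day draw and an early second draw could still convert afterwards. She would enter the SAP 10.5 table as a negative, indistinguishable from a woman sampled on schedule. Treatment-induced antibodies are a secondary safety endpoint, a response starts follow-up of up to one year (7.2.4), and neutralizing antibodies are among the events that may warrant considering trial termination (4.5). The timing of the negatives therefore matters to how the result is read.

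**Working it through.** **Inputs**

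| Step | Value | Source |
|---|---|---|
| Dosing after the trigger criterion | None: "Administration of FE 999049 or placebo after reaching the triggering criterion is not allowed" | Protocol 6.1.5 |
| Criterion to trigger | Same day: "Administration of hCG or GnRH agonist must take place the same day as the criterion for triggering of final follicular maturation" | Protocol 6.1.5 |
| Last dose to trigger, g | 0 or 1 calendar day (assumption; injections are daily) | Not stated |
| Trigger to retrieval, r | "36h ±2h after triggering"; taken as 2 calendar days (assumption, since no trigger clock time is given) | Protocol Table 6-1 |
| Retrieval to transfer | 5 days | Protocol 6.1.8.1 |
| Transfer to βhCG visit, k | 10, 11, 12, 13 or 14 days | Protocol 6.1.9.1 |

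**Check against the plan's own pairing.** Transfer day after last dose = g + r + 5. With g = 0 this is 0 + 2 + 5 = 7; with g = 1 it is 1 + 2 + 5 = 8. Both lie within 7-10 days, which reproduces the protocol's statement that the first sample may coincide with transfer.

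**βhCG visit.** Day after last dose = g + r + 5 + k.

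| g | Transfer day | βhCG days (k = 10 to 14) | Days in 21-28 | Days before 21 |
|---|---|---|---|---|
| 1 | 8 | 18, 19, 20, 21, 22 | 2 (k = 13, 14) | 3 of 5 |
| 0 | 7 | 17, 18, 19, 20, 21 | 1 (k = 14) | 4 of 5 |

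Put the other way, the 21-28 day window is transfer +13 to +20 when transfer is on day 8, and transfer +14 to +21 when it is on day 7. It overlaps the 10-14 day βhCG window only at the end.

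**Sensitivity**

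- *Clock time.* Section 6.1.5 says of the end-of-stimulation endocrine sample that "the blood sample must be drawn at least 8 hours after the latest administration of IMP and GnRH antagonist". Take 8 to 30 hours from last dose to trigger (the upper end is an assumption) and 34-38 hours to retrieval. The visit then runs from (8 + 34)/24 + 5 + 10 = 16.8 days to (30 + 38)/24 + 5 + 14 = 21.8 days.
- *Shorter.* With a trigger early in the day, retrieval can fall on the next calendar day (r = 1). With g = 1, transfer is on day 7 and 1 of 5 days is in window. With g = 0, transfer is on day 6, the visit is on days 16-20, and none is in window.
- *Longer.* Transfer on day 9 or 10 would put 3 or 4 of 5 days in window. With r = 2 that needs a gap of 2 or 3 days between last dose and trigger, which sits badly with daily dosing and the prohibition of coasting (3.1.2).

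**What follows after an early draw**

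- *βhCG positive.* The next scheduled visit is 35-48 days after transfer (6.1.10). That is day 7 + 35 = 42 to day 8 + 48 = 56 after the last dose, past day 28. No scheduled visit lies in the window.
- *βhCG negative.* Section 6.1.12 places end-of-cycle no earlier than the 21-28 day point, but asks for the antibody sample only if the second one has not been taken. Whether an early draw counts as taken is open to two readings.

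**The case against.** The strongest reply is that footnote k settles the matter. It makes 21-28 days mandatory, says only that the draw may coincide with the βhCG visit, and requires a separate visit otherwise, without limiting that to women who miss the βhCG visit. The same window recurs in 3.1.2, 6.1.9.2 and 7.2.4. A βhCG visit booked on transfer day +13 or +14 (day +14 if transfer is on day 7) satisfies every passage. For βhCG-negative women, 6.1.12 exempts only a sample taken as 6.1.9.2 describes, which can be read as still requiring an in-window draw.

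This stands as far as it goes. A reader might infer from the day count that most second samples will be out of window. The documents do not support that: permitted days are not women, sites may choose late days to combine visits, and footnote k gives a compliant route. Nor is 21-28 days part of the endpoint definition. It is a sampling schedule, and in women negative before dosing, any positive post-dosing sample counts as a response (7.2.4). An early draw loses only responses not yet detectable at either draw.

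A reader might also try to put a size on the bias. At the 1.1% first-cycle incidence in section 1.1, 500 × 0.011 = 5.5 cases are expected, so each missed case is 1/5.5 = 18% of that total. However, the documents do not say how many women have a fresh transfer, how many would be sampled early, or what share of responses first appears after days 17-20. Cancelled cycles, agonist triggers and retrievals of 20 or more oocytes bypass 6.1.9.1. The figure shows how few events there are; it does not estimate an effect. Section 1.3 also reports that earlier titers were undetectable or very low and non-neutralizing.

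The reply does not remove the conflict. Section 6.1.9.1 is an unconditional instruction, 6.1.9.2 describes the alternative draw only for women who do not attend that visit, and a βhCG-positive woman sampled early depends on a table footnote alone. SAP 10.5 lists assessments only for assay-2 positives. The general listing promise in SAP 10.1 may show dates for the others, but no summary separates early negatives from those on schedule.

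**Conclusion.** The protocol contradicts itself on the second antibody sample. Under the stated assumptions (last dose 0-1 day before trigger, retrieval two calendar days after it), the visit at which 6.1.9.1 orders the sample falls 17-22 days after the last dose, and 3 or 4 of its 5 permitted days precede the window set elsewhere. A site can comply with 6.1.9.1 and breach footnote k, with the clearest gap for βhCG-positive women.

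The finding is that early sampling is allowed by one instruction and would go unmarked in the summary. It is not that early sampling happened, nor that the antibody incidence is biased by a known amount. This is a contradiction worth correcting; it does not threaten the efficacy conclusion.

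**What to change.** **Protocol.** Reconcile 6.1.9.1 and 6.1.9.2 with Table 6-1 footnote k and 6.1.12, so that the sampling instruction and the 21-28 day window agree for women who attend the βhCG visit. The reconciled text should also state whether a draw outside the window counts as the second sample for 6.1.12.

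**SAP 10.5.** Flag second post-dosing samples taken outside 21-28 days after the last dose. Add a supportive row giving the proportion with treatment-induced antibodies among subjects with an in-window second sample. The main tabulation stays as it is.

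**Cost.** One extra table row and, for some women, the separate draw that footnote k already foresees. The Summary of Changes for Amendment 01 says that fresh cycles had been completed up to the ongoing pregnancy visit, so rewording cannot alter samples already drawn in this trial. The SAP change remains useful: it shows whether sites followed footnote k, and if they did not, it tells the reader which negatives rest on an early sample.
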